Assessment of BHB Concentration Agreement Among Sampling Locations and the Impact of Ketosis on Erythropoietin Levels: A Two-Part Study

Aim and perspective

This study's main goal (part 1) is to determine

- i. agreement in beta-hydroxybutyrate (BHB) of capillary and venous blood estimates and subsequently whether agreement is dependent on BHB level, and
- ii. agreement in BHB of finger and earlobe capillary samples, and
- iii. agreement in BHB of venous estimates (estimated by point-of-care device) and full blood (estimated by use of hydrophilic interaction liquid chromatography tandem mass spectrometry (HLCMS))

The main goal (part 2) is to determine

- i. effects of ketosis on erythropoietin(EPO) short-term and long-term
- ii. derived effects on erythropoiesis and iron metabolism from two-week intermittent ketosis

This study will establish (part 1) whether it is appropriate to select a specific sampling site for measuring BHB in patients and performing research, and whether there is a difference between measurements capillary and venous blood. The agreement between the KetoSure, a point-of-care-test (POCT) device, and the gold standard will also be examined, offering insight into any discrepancies with point-of-care estimates obtained by electrochemical estimations and HLCMS. High BHB measurement validity is required in both clinical and experimental contexts. First, BHB quantification may aid in clinical decision-making for suspected hyperinsulinemia, hypoglycemia of uncertain etiology, diabetic ketoacidosis, and other diseases. Second, a substantial amount of research has been conducted on BHB inference and ketones in general in recent years, and the validity of the interpretation of these studies is highly dependent on measurement precision in regards to which sample type and sampling site is applied.

In addition, the effects of ketosis on EPO concentrations will be investigated (part 2) from blood samples obtained during part 1 (acute effects) and at day 7 and day 14 where participants are intermittently ketotic allowing also for investigations on EPO-derived effects on erythropoiesis and iron metabolism.

Background

During an experiment in which samples were obtained from two distinct places, namely the finger pulp and the earlobe, the KetoSure ketonometer disclosed a discrepancy in BHB estimates, prompting us to review the relevant literature on discrepancy between sampling sites.

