The study day duration will be approximately four hours with participants reporting in at Klinik for Diabetes & Hormonsygdomme, Viborg Regional Hospital at 8 A.M. in the overnight fasted state. A standard 18G venous catheter is inserted in a median cubital, basilic, or cephalic vein for blood sampling. Baseline and following, blood samples are drawn on the hour for 3 hours. Subsequently, participation is over, the catheter is removed with observation and compression 5-10 min. upon which the study participation is over for the part of the participants.

Ambulatory investigations (part 2)

Following the study day (part 1) participants are provided the full amount of either the ketone monoester drink or the comparator (placebo-drink). The drinks are provided in small plastic bottles

Methods

In order to obtain ketosis, participants ingest a common sports drink, KE4, which contains a ketone monoester. Upon this, ketosis is established with a substantial increase in BHB for estimation in the venous and whole blood, along with capillary measurements from the earlobe and finger pulp. The dosage will be 500 mg/kg for the study day (part 1) and daily, divided in two or three dosages as preferred, for the following 14 days (part 2)

Feasibility

No substantial practical challenges are expected – all equipment and competences are present in the Department of Internal Medicine and Department of Clinical Biochemistry. No recruitment issues are expected – this is a small-scale study with minimal impact in relation to participation.

The study is fully funded by independent research funds within departments involved although external funding will be sought for.

Analytic methods

BHB is estimated by the Ketosure™ for capillary measurements (finger pulp and earlobe), for venous blood samples, and HLCMS for full blood estimation of BHB as the reference standard.

Statistical considerations

Analytical approach

Following a visual examination of the graphical representation for linearity, differences are calculated using the paired t-test, agreement is determined using the Bland-Altman plot, and Pearson's r is used to determine correlations. Supporting calculations are performed using Lin's concordance correlation coefficient of absolute agreement. When comparisons over observations from part 1 and 2 are performed an repeated measurements anova equivalent analysis is applied.

Sample size and power calculation

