No previous studies with data on BHB agreement have been performed. Based on our incidental findings, only very few subjects would be needed. The data is, however, far too small to base sample size calculations on.

Based on Boyd et al.[1] with highly correlated estimates of glucose and the acceptance of a type 1 error (α) of 0.05, type 2 error of 20% (β), a sample size of 13 participants is required to provide adequate statistical power to detect a difference of 0.58 mM in glucose estimates between capillary and venous blood samples with the standard deviation of 0.68 mM. Others have similarly found a clinically meaningful difference of 1 mM between sampling sites[8]. With α and β set as mentioned, a sample size of 20 participants is

required to provide adequate statistical power to detect a difference of 1 mM (SD = 1.5), should such a difference exist.

As such, we find it reasonable to include 15 patients in our study resulting in a power of 91% if expecting a meaningful difference of 1 mM and an average standard deviation of the two studies mentioned of 1.1 mM. Similar number of participants have been used elsewhere with regards to part 2 of this project and sample size as suggested is fully justified to test hypotheses of part 2.

Participants

Recruitment

Subjects will be recruited through notices on specific websites (sundhed.dk, forsøgsperson.dk) and social media (Facebook) along with board notice on selected local educational institutions, hospitals, and in newspapers.

First contact will be by telephone with the primary investigator(s) followed by the formal information on study participation (see section on recruitment and informed consent)

Inclusion criteria

Age 18-60 years

BMI 19-30 kg/m²

Expected ease of catheter insertion

Considered of sound health

Oral and written informed consent

Exclusion criteria

Inability to fully understand the consent including consent forms

Inability to cooperate to the study

Any electrolyte disorders, kidney disease or otherwise compromised renal function including excess risk hereof, e.g. hypertension, albuminuria, autoimmune disease, family history of kidney disease

Any liver or bile disease, or an increased risk of getting one, such as from hepatotoxic drugs, alcoholism, gallstones, pancreatitis, an autoimmune disease, or a history of liver disease in the family.

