Diabetes mellitus or any metabolic and/or hormonal disease including diagnosed/undiagnosed reactive hypoglycemia or similar disorders. This includes treatment with drugs, and dietary supplements with inference on key metabolic or hormonal markers, e.g. insulin, glucagon, lipids, and GLP-1

Any use of illegal or otherwise use of medicinal products without prescription

Anemia or other known disease of the hematopoietic system

Previous bariatric surgery

Previous myocardial infarction or uncontrolled myocardial ischemia

Recent intended/unintended weight loss

Allergies to catheters or adhesives

Safeguards to minimize pain, discomfort, fear and other risks

Short-term and long-term risks and side effects

There are neither short-term nor long-term serious hazards or adverse effects to concern.

KE4 is a bitter sports drink that can cause moderate, temporary nausea and bloating.

Appetite may be slightly reduced over the full study period (part 2). Compared to sweet, salty, or umami-flavored beverages, the digestive adverse effects are equivalent to those of bitter-flavored beverages in general. This is a well-known side effect of bitter-tasting beverages in certain individuals.

As with the pricking of the fingers and earlobes, there is a small risk of infection following catheter placement, as well as a slight degree of discomfort.

Risk of radioactive radiation

There is no radiation involved in this study

Collection of new biological material

What and how much material

A total of 150 mL of blood is drawn in this study. This includes unavoidable spill from repeated sampling from indwelling catheter in part 1. No spillage is associated with part 2 since blood sampling is performed only twice in an outpatient setting (at the hospital laboratory for blood sampling)

Purpose

For analysis in bulk.

How long and what is the purpose of storage

All biological samples are stored for the full period of data collection and 18 months after in order to analyse all samples in bulk. Samples are stored at -80 °C.

Biobank

A research biobank is developed for the bulk analysis of all samples not analyzed on the day of the study, i.e. measurements using the Ketosure™ POCT device. The analyses are conducted within a few months at the earliest opportunity and surplus material is preserved as a biobank for future yet undetermined research.

Information from patient records

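### Eligibility criteria do not address pregnancy or breastfeeding, so a healthy pregnant or breastfeeding volunteer could be enrolled and given the ketone drink

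*Combined protocol and SAP*

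**What the plan says.** **Who may enter.** The Inclusion criteria section sets "Age 18-60 years", a BMI range, ease of catheter placement, "Considered of sound health" and consent. It has no criterion on sex.

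**Who is kept out.** The Exclusion criteria section is detailed. It reaches as far as kidney or liver disease in the family, earlier bariatric surgery and allergy to adhesives. The two entries closest to this point are "Diabetes mellitus or any metabolic and/or hormonal disease including diagnosed/undiagnosed reactive hypoglycemia or similar disorders" and "Anemia or other known disease of the hematopoietic system". Pregnancy, breastfeeding, contraception and pregnancy testing appear nowhere in the supplied text.

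**What participants take.** Under Methods, the ketone drink is taken on the study day and then "daily, divided in two or three dosages as preferred, for the following 14 days (part 2"). The Design section randomises Part 2 participants 1:1 to the ketone drink or a matched placebo.

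**What is said about risk.** The section on short-term and long-term risks states: "There are neither short-term nor long-term serious hazards or adverse effects to concern".

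**What Part 2 measures.** The aims are "effects of ketosis on erythropoietin(EPO) short-term and long-term" and "derived effects on erythropoiesis and iron metabolism from two-week intermittent ketosis".

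**The concern.** Recruitment is open to the public through websites, social media, educational institutions, hospitals and newspapers. Nothing restricts it to men or to women past childbearing age. A healthy, non-anemic pregnant or breastfeeding woman has no disease in the sense of the exclusion list, so its wording does not remove her.

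Two things are at stake. The first is safety: she would take the drink although the documents offer nothing to support exposure in pregnancy. By its title, the cited study of oral ketone monoester and EPO was done in healthy men. The second is the science of Part 2. Excluding anemia and blood-forming disease suggests that the authors wanted other influences on EPO, red cells and iron kept out. If pregnancy or breastfeeding also bears on those outcomes (an assumption here, since the documents do not discuss it), the same reasoning was not carried through.

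**Working it through.** **1. Does any criterion remove her?**

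| Criterion | Does it exclude a healthy pregnant or breastfeeding woman? |
|---|---|
| Age 18 to 60, BMI 19 to 30 | Not in itself |
| Sound health | Not by its terms; it is undefined and leaves the decision to the investigator |
| Metabolic or hormonal disease | No; worded as disease |
| Anemia or blood-forming disease | Only if she is anemic or has such a disease |
| Recent weight loss | Only if it applies to her |
| Interview and examination before consent (Recruitment of participants and informed consent) | Content not given; may be held by video call; no question or test required |

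Some such women would be removed incidentally. None would be removed because of pregnancy or breastfeeding.

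**2. What would she be exposed to?** As the text reads, the study-day drink goes to every participant. In Part 2, 1:1 allocation gives a probability of 1/2 of the ketone drink for 14 further days and 1/2 of placebo. The scheduled contacts in that period are days 7 and 14.

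**3. The plan's own figures.** The stated sample sizes and power reproduce with a two-sided paired t-test at 0.05:
- 0.58 mM with SD 0.68 needs 13 participants.
- 1 mM with SD 1.5 needs 20 participants.
- At n = 15 and 1 mM, power is 90.5% with SD 1.1 and 91.0% with SD 1.09 (the mean of 0.68 and 1.5), against the stated 91%.

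These concern the Part 1 paired comparison and are unaffected by this point. Part 2 has no calculation of its own. Fifteen at 1:1 gives arms of 7 and 8. A two-sample t-test then has 43% power at a difference of 1 SD and needs about 1.57 SD for 80%.

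**4. How far could one atypical participant move an arm?** The documents give no effect of pregnancy on EPO or iron, so the deviation k is assumed to be 1 to 3 SD. At a single time point the mean shift is k/n and the expected arm SD is multiplied by √(1 + k²/n).

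| k (SD) | Shift, n = 7 | SD factor, n = 7 | Shift, n = 8 | SD factor, n = 8 |
|---|---|---|---|---|
| 1 | 0.14 | 1.07 | 0.13 | 1.06 |
| 2 | 0.29 | 1.25 | 0.25 | 1.22 |
| 3 | 0.43 | 1.51 | 0.38 | 1.46 |

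Expressed as a ratio, one participant with EPO m times that of the others shifts the raw mean by (m − 1)/n. For an assumed m of 2 to 3 this is 1/7 to 2/7, or 14% to 29%, in an arm of 7, and 1/8 to 2/8, or 12.5% to 25%, in an arm of 8.

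**5. Does that carry over to the planned analysis?** The plan draws a baseline sample and uses a repeated-measures analysis across Parts 1 and 2. With a stable additive offset c, her change is (Y₁ + c) − (Y₀ + c) = Y₁ − Y₀, so the shift in mean change is 0. The offset matters only if her level drifts over the 14 days or her response differs in size. If her level and her response are both multiplied by m, the mean change on the raw scale again shifts by (m − 1)/n, while on a log scale it cancels. The documents do not say which case applies.

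**The case against.** The strongest reply is that screening exists. Investigators interview and examine each volunteer before consent, and the sound-health criterion lets them decline a pregnant woman. The consent pages are not in the supplied text and may address pregnancy. This stands in part: enrolment is not automatic. But no rule or check is required, a volunteer may not know of an early pregnancy, and a line in a consent form would not make it an eligibility criterion. That women are eligible is itself inferred from the absence of a sex criterion.

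It can also be said that the hazard statement describes enrolled participants, so its scope simply follows the criteria. That is fair, and it is why the gap in the criteria is the main defect.

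Three stronger readings are tempting, and the documents do not support them:
- **That one pregnant participant would distort Part 2, by 14% to 29%.** The two- to three-fold input is not in the documents, the figure is a raw-mean shift at one time point, and a stable offset largely drops out of comparisons with baseline. Randomisation also makes her roughly equally likely to fall in either arm, so the expected effect is noise and not systematic bias.
- **That she would certainly take the ketone drink for 14 days.** Half of the Part 2 allocations are to placebo.
- **That the drink is harmful in pregnancy.** The documents show neither harm nor safety.

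**Conclusion.** The omission is real and should be corrected. As written, the criteria admit a healthy pregnant or breastfeeding volunteer. She could receive the ketone drink on the study day and, with probability 1/2, for 14 further days at home, with no supporting basis in the documents. The safety argument is sufficient by itself.

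The effect on the results is secondary. With arms of 7 and 8, such a participant could add noise to EPO, erythropoiesis and iron outcomes. Its size is unknown: the shifts in the working rest on assumed deviations and are illustrative only, and for a stable offset the effect on change from baseline is close to zero. No power or sample-size figure in the plan changes. The conclusion rests on the two criteria lists being complete as supplied, which they appear to be.

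**What to change.** - Add pregnancy and breastfeeding to the exclusion criteria.
- State that status is confirmed before the first drink, with the method left to the investigators. The stored baseline blood is not suitable for this: under Collection of new biological material and Biobank, samples other than same-day Ketosure readings are held for bulk analysis, so no result would be available in time.
- Limit the statement on serious hazards to the population that is eligible under the amended criteria.

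The cost is one question or simple test per woman who could be pregnant, plus a few lines of text. The effect on recruiting 15 volunteers should be negligible, and the analysis plan needs no change.
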